4.13.3 Adverse Events

As per the International Council for Harmonisation (ICH) guidelines, an AE is any untoward medical occurrence in a subject or clinical investigation subject administered a

pharmaceutical product and which does not necessarily have a causal relationship with this treatment. An AE can, therefore, be any unfavorable and unintended sign (including an abnormal, clinically significant laboratory finding), symptom, or disease temporally associated with the use of a medicinal (investigational) product, whether or not considered related to the medicinal (investigational) product. Bleeding events will not to be considered as AEs but are to be documented as a bleeding event in the subject's electronic diary (eDiary).

Any AE reported as resulting in death, immediate risk of death (life threatening), inpatient hospitalization or prolongation of existing hospitalization, persistent or significant disability/incapacity, or a congenital/anomaly/birth defect will be classified as a serious adverse event (SAE). An SAE may also be any other medically important event that, in the opinion of the Investigator, may jeopardize the subject or may require intervention to prevent 1 of the other outcomes listed above.

Adverse events (AEs) will be coded and grouped by system organ class (SOC) and preferred term (PT) using the Medical Dictionary for Regulatory Activities (MedDRA) Version 21.0 for PTPs and Version 23.1 or higher for PUPs.

An AE will be regarded as treatment emergent (TEAE) for this study if it was present before the first dose of rIX-FP in this study and subsequently worsened in severity, or was not present before the first dose but subsequently appeared. For this determination, partially missing dates will be handled as outlined in [Table 1](#). An AE will be assumed to be treatment-emergent if non-treatment emergence cannot be reasonably ruled out. In order to reflect the adverse event profile with routine prophylaxis treatment, summaries of TEAEs will exclude AEs during the surgical period and subcutaneous substudy. TEAEs during those periods will be presented separately. TEAEs will be summarized separately for subjects in PUPs and PTPs.

Adverse events will be recorded from the time when informed consent is granted at the start of this extension study until study completion (or the end of study visit upon early termination). In this study, treatment-emergent AEs are defined as those with onset on or after Day 1 in this study.

Related AEs are AEs considered by the investigator to be related to study treatment.

TEAEs leading to withdrawal from study or withdrawal from study medication are any TEAEs reported on the AE log with "Was subject terminated from study due to the AE" as "Yes" or "Action taken with study drug" with response of "Permanently discontinued" respectively.

Adverse events of special interest (AESI) will include preferred terms associated with the following Standard MedDRA Queries (SMQs) based on narrow search criteria:

1. Anaphylactic reactions
2. Embolic and thrombotic reactions
3. Hypersensitivity

AEs will be reported separately for the surgery substudy, subcutaneous substudy, main study (prophylaxis and PK period), and overall (all periods). The following will be summarized by SOC and PT for the number and percentage of subjects who experience at least 1 event and the total number of events:

- all AEs including AESIs
- all SAEs
- TEAEs, overall and by regimen
- related TEAEs
- TEAEs occurring \leq 72h after infusion of study medication
- non-serious TEAEs
- SAEs
- related treatment-emergent SAEs
- TEAEs by maximum severity (If a subject experiences multiple events that map to a single PT, only the most severe event will be counted.)
- TEAEs by highest relationship and maximum severity (If a subject experiences multiple events that map to a single PT, only the related event and the most severe will be counted.)
- TEAEs leading to withdrawal of study medication
- TEAEs leading to death
- TEAEs by every six-month time intervals (not applicable for PUPs)

SOCs will be displayed by decreasing frequency, and PTs will be displayed in decreasing frequency by subject.

TEAEs also will be presented for the following subgroups:

- subjects \geq 18 years who switched from 14-day regimen to 21-day regimen
- subjects \geq 18 years who switched to 21-day regimen compared with subjects \geq 12 years not switching
- subjects $<$ 12 years in 14-day regimen
 - paired subjects who had 7-day and 14-day regimen in CSL654_3003
 - subjects in CSL654_3003 14-day regimen
 - subjects in CSL654_3002 who had 14-day regimen in CSL654_3003

- subjects <12 years who switched to 14-day regimen compared with subjects <12 years not switching

TEAEs will be counted in the respective regimen based on the onset time of the TEAE.

Adverse events associated with COVID-19 will be summarized for PUPs. These events will be identified based on predefined terms from SMQs as described above. An overall summary and a summary of TEAEs by SOC and preferred term will be provided. A supportive listing of adverse events associated with COVID-19 will be included.

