9.1.2 Adverse Events of Special Interest

There are several AEs that will be monitored closely as adverse events of special interest (AESIs) to enable an adequate risk-benefit evaluation of rIX-FP versus standard therapy during the study and additional data may be requested for these events. The AESIs will be:

- AEs associated with confirmed (ie, with second blood sample) inhibitor formation.
- Thrombotic and / or embolic events.
- Anaphylaxis.

AESIs should be considered medically significant and are therefore SAEs. The expedited reporting procedures for SAEs are described in detail in [Section 9.6](#).

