11.3.3.2 Adverse Events

Adverse events will be recorded from the time when informed consent is granted at the start of this extension study until study completion (or the end of study visit upon early termination). In this study, study-emergent AEs are defined as those with onset on or after Day 1 in this extension study.

Adverse events will be coded using the Medical Dictionary for Regulatory Activities (MedDRA). The number and percentage of subjects who experience AEs will be summarized overall by system organ class (SOC) and preferred term (PT) and will also be summarized based on maximum severity and relationship to rIX-FP.

Descriptive analysis of AEs will include:

- Incidence of study-emergent AEs, AESIs and SAEs grouped by SOC and PT.
- Incidence of study-emergent AEs, grouped by SOC and PT, with reference to the relationship to rIX-FP and maximum severity.
- Incidence of study-emergent AEs leading to withdrawal grouped by SOC and PT.
- Incidence of related AEs to rIX-FP over the course of the study.

Individual listings of all AEs will also be provided.

Serious AEs, deaths, and discontinuations due to AEs will be summarized and supported by individual subject data listings.

A summary of study-emergent AEs by SOC and PT will be provided by treatment interval. Subjects who change the frequency of dosing during the duration of this extension study may be counted more than once in this summary.

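### SAP 4.13.3 leaves inhibitor-associated adverse events out of its AESI definition without declaring the change, and does not say which terms identify COVID-19 adverse events

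*SAP*

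**What the plan says.** **AESIs.** Protocol 9.1.2 lists three categories: "AEs associated with confirmed (ie, with second blood sample) inhibitor formation", "Thrombotic and / or embolic events", and anaphylaxis. It adds: "AESIs should be considered medically significant and are therefore SAEs". Protocol 11.3.3.2 plans this summary: "Incidence of study-emergent AEs, AESIs and SAEs grouped by SOC and PT".

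SAP 4.13.3 defines the set differently: "Adverse events of special interest (AESI) will include preferred terms associated with the following Standard MedDRA Queries (SMQs) based on narrow search criteria". The queries are anaphylactic reactions, embolic and thrombotic reactions, and hypersensitivity. The AESI entry in its list of SOC and PT summaries reads "all AEs including AESIs". SAP section 8, which lists departures from the protocol separately for previously treated patients (PTPs) and PUPs, does not mention AESIs in either list.

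**COVID-19.** At the end of SAP 4.13.3: "Adverse events associated with COVID-19 will be summarized for PUPs". The selection rule follows: "These events will be identified based on predefined terms from SMQs as described above".

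**The concern.** An AESI list fixes in advance which safety events get separate attention. Here the SAP's list differs from the protocol's, and the dropped category is the one closest to the study's primary objective, which is new cases of FIX inhibitors. A programmer working from the SAP has no instruction to flag an adverse event reported with a confirmed inhibitor. At stake is the content of the AESI flag and of any summary built on it.

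The added hypersensitivity query causes a smaller difficulty. Protocol 9.1.2 treats every AESI as serious, but a narrow hypersensitivity query could flag an event that was reported as non-serious.

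The COVID-19 sentence is a separate fault in the same section. Its cross-reference does not lead to any COVID-19 terms, so the planned table cannot be programmed as intended from the text.

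**Working it through.** The plan gives no figure to reproduce. The check compares the two definitions, traces the cross-reference, and sizes one case.

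**Step 1: the two AESI definitions.**

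| Category | Protocol 9.1.2 | SAP 4.13.3 |
|---|---|---|
| Adverse events tied to a confirmed inhibitor | Yes | No |
| Thrombotic or embolic events | Yes | Yes (narrow SMQ) |
| Anaphylaxis | Yes | Yes (narrow SMQ) |
| Hypersensitivity | No | Yes (narrow SMQ) |

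Two of the protocol's three categories carry over, one is dropped and one is added. The surgery substudy safety variables in SAP 6.6 mention AESIs, but the SAP gives no second definition.

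**Step 2: is the change declared?** In SAP section 8, the PTP entries cover the added subgroup analyses, the added exposure-day endpoint, the negative binomial model, and the handling of time after surgery. The PUP entry covers bleeding rates only. Neither declares the AESI change.

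**Step 3: where do inhibitor events still appear?**
- SAP 4.13.1 makes inhibitor development the primary safety endpoint. SAP 4.13.2 gives it a laboratory definition (at least 0.6 BU/mL, confirmed on retest, both tests by a central laboratory), a PUP-specific incidence, and Wald and Clopper-Pearson intervals.
- An adverse event reported with an inhibitor enters the overall AE tables. If it is reported as protocol 9.1.2 and 9.5.2 require, it also enters the SAE tables.
- It does not enter an AESI set built from the three queries, assuming that its preferred term lies in none of them. MedDRA query contents are not in the documents, so this is an assumption.

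**Step 4: size of one missed case.** Protocol 3.5 and SAP 3.3 plan at least 13 PUPs. Let N be the number of PUPs in the safety population. A subject whose only AESI is inhibitor-associated changes AESI incidence by 1/N. At N = 13:

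1/13 = 0.077, or 7.7 percentage points.

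This is the per-case effect on the flag at minimum enrolment. It falls as N rises, and it is zero for a subject who has another event inside the three queries. The incidence in SAP 4.13.2 does not change, because it has its own numerator and denominator (PUPs with at least 50 exposure days, plus those with fewer who have a confirmed inhibitor).

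**Step 5: the COVID-19 cross-reference.** The only queries named earlier in SAP 4.13.3 are the three AESI queries, and none is a COVID-19 query. The one explicit COVID-19 search rule in the SAP is in 4.4. It matches COVID or Coronavirus in the free text of other discontinuation reasons, and does not apply to adverse event terms. SAP 4.9 plans a summary of medications given for COVID-19 adverse events but does not say how those events are identified. It is reasonable to infer, though not stated, that it depends on the rule in 4.13.3.

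**The case against.** **Inhibitors are fully reported elsewhere.** This stands, and it limits the point to the AESI classification. It does not remove it. SAP 4.13.2 reports a laboratory-defined incidence on a restricted denominator, whereas protocol 11.3.3.2 plans AESIs as adverse events by SOC and PT.

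**The SAP's wording need not be exhaustive, and SAP precedence over the protocol covers only statistical methods.** On this reading the queries cover term-coded AESIs and the laboratory covers inhibitors. That is possible, but the SAP does not say so and gives no other AESI criterion.

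**The SAP names no standalone AESI table.** Correct. Its only line is "all AEs including AESIs", and SAP 9.2 leaves the table list to a separate document. What can be said is that the flag, and the AESI incidence that the protocol plans, would be incomplete.

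**The COVID-19 sentence probably describes a method, with the query left out by oversight.** This is the likelier reading. It still leaves the events unidentified.

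**Scope is narrow.** SAP 3.1 says PTPs have already been reported, and SAP 4.1 makes the PUP analyses descriptive. Both are true, so the change mainly affects PUP outputs.

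A reader might also infer that the AESI output would contradict the SAE listing. It would not. The protocol makes AESIs a subset of SAEs, so an inhibitor event that is an SAE without an AESI flag breaks no subset rule.

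**Conclusion.** The point holds in two limited parts.

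1. The SAP's AESI definition omits a protocol category and adds another, and neither change is declared. The AESI flag and the AESI incidence in protocol 11.3.3.2 would exclude inhibitor-associated adverse events. The per-case effect is at most 7.7 percentage points at 13 PUPs. This assumes that the subject has no other AESI and that the inhibitor term falls outside the three queries.
2. The COVID-19 rule does not identify the intended events, because no COVID-19 query or term list precedes it.

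Two stronger conclusions are not supported. One is that the study would fail to report its main safety event; the primary inhibitor analysis and the AE and SAE tables are intact. The other is that the COVID-19 table deliberately selects the wrong events or would show a count of zero. An omitted query is more plausible than deliberate selection. Read literally, the rule would collect whatever matches the three AESI queries, and that depends on MedDRA content that the documents do not give.

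This should be corrected, but it does not threaten the primary analysis.

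**What to change.** In SAP 4.13.3:
- Add an AESI category for adverse events associated with confirmed FIX inhibitor formation, citing protocol 9.1.2. Link it to the laboratory definition in SAP 4.13.2. The 0.6 BU/mL threshold and the central-laboratory requirement come from 4.13.2; protocol 9.1.2 asks only for confirmation on a second blood sample.
- Show hypersensitivity as a separately labelled SAP addition, so that the protocol's AESI categories can be read on their own.
- Replace the back-reference in the COVID-19 paragraph with a named query or term list and its MedDRA version. Use the same list for the COVID-19 medication summary in 4.9.

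In SAP section 8, declare the handling of the inhibitor category and the hypersensitivity addition.

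The cost is a few sentences and changes to two event flags before database lock. No new data are needed. If the database is already locked, section 8 provides for describing and justifying departures from the SAP in the clinical study report, and the same changes can be made there.

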14.7 CLINICAL STUDY REPORT

A final clinical study report will be written after the completion of the study. In addition, study reports will be written when a) all subjects have completed the SC substudy and b) when all PTPs have completed the study (see [Section 11.3.6](#)). These reports will be integrated into the final clinical study report.

CSL or its agent will write the report in consultation with the investigator or, if applicable, a nominated coordinating investigator (or delegate). It is required by CSL that the coordinating investigator will sign the clinical study report.

Progress reports may be provided to the relevant regulatory bodies in accordance with their requirements.

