This document presents the statistical analysis plan (SAP) for CSL Behring GmbH, Protocol No. CSL654_3003: A Phase 3b Open-label, Multicenter, Safety and Efficacy Extension Study of a Recombinant Coagulation Factor IX Albumin Fusion Protein (rIX-FP) in Subjects with Hemophilia B.

This analysis plan is based on the protocol amendment 6 dated 03 February 2020, final electronic case report form (eCRF) dated 17 May 2017, and the SAP version 3 dated 20 April 2018. This SAP contains all analyses for the previously treated patients (PTPs), and the updated contents for the previously untreated patients (PUPs).

In the event that the statistical methods specified in this SAP differ from those specified in the protocol, the statistical methods specified in the SAP will supersede the statistical methods described in the protocol.

2 Study Objectives

- Main Study
 - Primary Objective
 - The primary objective of this study is to evaluate the safety of rIX-FP as measured by new cases of inhibitors against FIX in subjects, including PUPs, with severe hemophilia B. The PK parameters in PUPs will also be collected.
 - Primary Endpoint(s)
 - The total number of subjects who develop inhibitors against FIX during the approximately 5-year participation in this study.
 - PK parameter of incremental recovery (IU/dL per IU/kg) of 50 IU/kg rIX-FP (Arm 4 only)
 - Secondary Objective(s)

[figure not shown]
The secondary objectives of the study are:

 - To evaluate the efficacy of rIX-FP routine prophylaxis when administered at various treatment intervals.
 - To compare the efficacy of rIX-FP routine prophylaxis between 2 different treatment intervals and versus on-demand treatment.
 - To further evaluate the safety of rIX-FP.
 - To evaluate the efficacy of treatment for bleeding episodes in PUPs.
 - Secondary Endpoint(s)
 - Annualized bleeding rate (ABR) for spontaneous treated and total treated bleeds for each assigned treatment interval (7 days, 10 days, 14 days, and 21 days).
 - Comparison of the annualized spontaneous bleeding rate (AsBR) and ABR between:

- 14-day routine prophylactic treatment in this study compared with on-demand only treatment from Study CSL654_3001 Arm 2.
- 7-day prophylaxis regimen with the 14-day prophylaxis regimen.
- 7-day prophylaxis regimen with the extended prophylaxis regimen (10-day or 14-day).
- Total number of exposure days of rIX-FP
- Consumption of rIX-FP during routine prophylaxis expressed as IU/kg per month per subject.

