3.1 Discussion of Study Design

This is a prospective, open-label, multicenter, non-randomized, phase 3b study to investigate the long-term safety and efficacy of recombinant coagulation factor IX albumin fusion protein (rIX-FP) for the routine prophylaxis and on-demand treatment of bleeding events in subjects with severe hemophilia B. Subjects will be eligible to enter the study if they are PUPs and meet the eligibility criteria (i.e. Arm 4).

Subjects who completed studies CSL654_3001, CSL654_3002, or any other CSL sponsored rIX-FP (CSL654) studies (i.e. Arm 1 and Arm 2) and meet the eligibility criteria, or subjects who have not previously completed a CSL sponsored rIX-FP lead-in study and meet the eligibility criteria (i.e. Arm 3) have already been analyzed in the clinical study report (CSR) dated 14 March 2019. These subjects will not be analyzed in this PUP study.

The study overview is provided in [Figure 1](#). A complete overview of the study design and rationale is provided in [Protocol CSL654_3003, Section 3.1](#).

Figure 1. CSL654_3003 Study Overview

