3.4 Study Arms

This study will include the following study arms:

Previously Treated Patients:

Arm 1: Subjects who have completed Study CSL654_3001 Arm 1, Study CSL654_3002, or any other CSL-sponsored rIX-FP (CSL654) lead-in study will administer rIX-FP once every 7, 10 or 14 days.

Arm 2: Subjects who were enrolled in Study CSL654_3001 Arm 2 and have <26 weeks of experience with rIX-FP will administer rIX-FP once every 7 days. Subjects who have ≥26 weeks of experience with weekly prophylaxis rIX-FP will administer rIX-FP once every 14 days.

Arm 3: Subjects who have not previously completed a CSL-sponsored rIX-FP lead-in study and who are scheduled to have a major non-emergency surgery within approximately 8 weeks from receiving the first rIX-FP injection (i.e., during the pharmacokinetics [PK] evaluation period) will administer rIX-FP once every 7 days until the month-6 visit.

After the month-6 visit, all subjects (Arms 1, 2, and 3) will administer rIX-FP once every 7, 10, 14 days, 21 days, or 3 times per month for approximately 30 months.

Note: All subjects in Arm 3 will undergo an initial rIX-FP (100 IU/kg) PK evaluation period and complete a surgery substudy before having the option to start routine prophylaxis. In addition, a subcutaneous (SC) substudy will evaluate the safety and PK of SC administration of rIX-FP in adults with severe hemophilia B who are enrolled in the main CSL654_3003 study.

Previously Untreated Patients:

Arm 4: PUPs with severe Hemophilia B (coagulation factor IX (FIX) activity ≤2%) who have never been treated with FIX clotting factor products (except previous exposure to blood components) will be enrolled. Subjects in Arm 4 will administer rIX-FP as weekly prophylaxis and/or on-demand during the first 12 months, and then continue on weekly routine prophylaxis.

This SAP is focusing on the statistical analyses on patients in Arm 4.

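### Minor, previously treated patients only (already reported in 2019): SAP 4.13.3 shows adverse events by regimen as counts and percentages with no rate per patient-year, although time on regimen can differ by years

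*SAP*

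**What the plan says.** **Metric.** SAP 4.13.3 lists a set of TEAE tables, one of them overall and by regimen, to be "summarized by SOC and PT for the number and percentage of subjects who experience at least 1 event and the total number of events". Each TEAE goes to the regimen in force at its onset. Under SAP 4.1 the percentage denominator is all subjects in that regimen. Protocol 11.3.3.2 likewise plans a summary by treatment interval without a rate, and notes that subjects who change frequency may appear more than once.

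**Subgroups.** For the paired and switcher groups, SAP 4.13.3 says only "TEAEs also will be presented for the following subgroups". One example is "subjects <12 years who switched to 14-day regimen compared with subjects <12 years not switching". No statistic is named there, and no period is given for subjects who did not switch. SAP 9.2 puts the list of tables, which accompanies the shells, in a separate document.

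**Scope.** SAP 3.1 says of Arms 1 to 3 that they "have already been analyzed in the clinical study report (CSR) dated 14 March 2019. These subjects will not be analyzed in this PUP study", and SAP 3.4 adds: "This SAP is focusing on the statistical analyses on patients in Arm 4". The SAP introduction nevertheless says the document holds all the PTP analyses. Protocol 14.7 says of the substudy and PTP reports: "These reports will be integrated into the final clinical study report".

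**Related plans.** SAP 4.7 derives accumulated days on each regimen and tabulates them by regimen and for largely the same subgroups. SAP 4.13.3 also has a PTP table of TEAEs by six-month interval, not stated to be split by regimen or expressed per time at risk.

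**The concern.** The share of subjects with at least one event, and the number of events, both grow with time observed. If two regimens have the same underlying rate but different time on treatment, the one observed for less time shows fewer events and a lower percentage. A reader comparing columns cannot separate rate from follow-up.

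Unequal time is a consequence of the design rules:

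- PTP participation is expected to last about 5 years, or until 100 exposure days (Protocol 3.3).
- The interval may change at each 6-month visit, and sooner for safety (Protocol 3.2.1.2).
- First use of the 21-day interval requires at least 6 months on 14 days (Protocol 3.1.2).
- A subject who does not benefit may leave the 21-day interval at any time (Protocol 1.4).

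The SAP does standardize other by-regimen outcomes for time. Bleeds are annualized and modelled with a log-time offset (SAP 4.12.3 and Table 3), and consumption is given per month and per year (SAP 4.11). SAP section 8 records that safety and efficacy analyses of the 21-day regimen, and of under-12s on 14 days, were added to explore these longer intervals. They are the groups for which a time-standardized safety figure would be most useful.

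**Working it through.** There is no stated figure to reproduce. The documents give neither time on each regimen nor adverse event rates for this study, so the rates, times and group sizes below are assumptions.

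**Model.** With a constant rate r per year and t years on regimen, the proportion with at least one event is 1 − exp(−r × t). Expected events among n subjects are n × r × t.

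**Same rate, different time:**

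| Rate per year | 0.5 y | 1 y | 2 y | 4.5 y |
|---|---|---|---|---|
| 0.2 | 9.5% | 18.1% | 33.0% | 59.3% |
| 1.0 | 39.3% | 63.2% | 86.5% | 98.9% |

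At 0.2 per year and 1 versus 2 years: 1 − exp(−0.2) = 0.181 and 1 − exp(−0.4) = 0.330. The pair 0.5 versus 4.5 years (the two add to 5 years) is an extreme example. It gives 10% versus 59% at the lower rate, and event counts differ 4.5 / 0.5 = 9-fold.

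**Any TEAE, anchored on the phase 1/2 study.** Protocol 1.2.3.2 reports 46 TEAEs, with 14 of 17 subjects affected, over roughly 11 months of evaluation after a short PK period. Taking 11 months for each subject (longer stays would lower both rates):

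- By count: 46 / (17 × 11/12) = 2.95 per year.
- By proportion: −ln(1 − 14/17) / (11/12) = 1.89 per year.

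At 1.89 to 2.95 per year, the share with any TEAE is 61–77% at 0.5 years, 85–95% at 1 year and 98–99.7% at 2 years. The overall percentage soon nears its ceiling and says little about rate, while the event count keeps growing with time.

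**What a rate would show.** Take 10 subjects per regimen at 0.2 per year:

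- 1 year each: 10 × 0.2 × 1 = 2 events in 10 patient-years, 0.20 per patient-year (exact Poisson 95% CI 0.02 to 0.72).
- 2 years each: 10 × 0.2 × 2 = 4 events in 20 patient-years, 0.20 per patient-year (0.05 to 0.51).

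The count doubles but the rate does not move, and the intervals show how little information either group carries.

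**The case against.** **The analysis is finished.** The PTPs were reported in March 2019, SAP 3.1 says they will not be analyzed again, and the Amendment 6 entry in the protocol's revision history says PTP text was kept only to avoid reworking the document. Integrating a report is not re-analyzing it. This stands as a limit on priority: no pending PTP decision changes, and a new table would be a post hoc addition. It does not make the planned metric adequate in a SAP that still carries all PTP analyses, or in a final report that will integrate the PTP results.

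**A reader can do the division.** Event totals from SAP 4.13.3 over times from SAP 4.7 give a crude rate. This is largely true. It yields no interval, however, and numerator and denominator may not match: TEAE summaries leave out the surgical and subcutaneous substudy periods, while SAP 4.7 does not say that time on regimen does so.

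**Safety is descriptive.** SAP 4.13 plans no formal safety comparisons unless specified, and counts with percentages are ordinary adverse event tables. Bleeding rates are secondary efficacy endpoints, so annualizing them creates no strict inconsistency. Both points stand, and they are why this is an improvement rather than an error.

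**The shells may already contain rates.** A reader might infer that the paired and switcher displays omit a rate. The documents do not support that, because the SAP names no statistic there and the shells are separate. The stated omission is in the by-regimen table.

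**The extreme case is not a boundary.** A reader might take 0.5 versus 4.5 years as a limit set by the protocol. It is not: stays can be shorter than 6 months, the prior 6 months on 14 days need not fall within this study, and 5 years is approximate.

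**Conclusion.** The point holds as a minor, inexpensive improvement for PTPs only. The plan states counts and percentages by regimen, and time on regimen can differ by years, so those columns mix event rate with follow-up. Under assumed constant rates a modest gap of 1 versus 2 years gives 18% versus 33% at 0.2 events per year, and 63% versus 87% at 1 per year. Actual time on each regimen is not in the documents, so the real distortion could be smaller or larger.

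A reader might also infer that the displays make longer intervals look safer. Nothing supports a direction, because either regimen may be the one observed for less time. The multi-interval comparisons do not concern Arm 4, where routine prophylaxis is weekly. The primary inhibitor endpoint and the study-wide adverse event endpoint are unaffected.

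**What to change.** Add one supplementary PTP table giving overall, related and serious TEAEs per patient-year by regimen, with exact Poisson 95% confidence intervals, labelled descriptive and non-randomized. Check the shells for the paired and switcher groups. If they lack a rate, extend the table to them; if they have one, a line in the SAP saying so is enough.

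The text should settle four things:

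- The denominator is time in the SAP Table 2 regimen periods. SAP 4.2 calls the periods disjoint for efficacy analyses, so say that they apply to these rates too.
- Surgery and subcutaneous substudy time is excluded once, from numerator and denominator alike.
- Which period counts for subjects who did not switch.
- Where events arising in a pharmacokinetic period are placed.

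A count model is unnecessary for groups this small.

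The cost is a little programming on a closed dataset, using periods the SAP already defines. The rates remain limited. Intervals were chosen on efficacy, safety, compliance or preference, and first 21-day use always follows 14-day use, so selection and ordering remain. A single rate is a fair summary only if the rate is roughly constant over time. The Poisson interval treats repeat events in one subject as independent and can be too narrow.
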